2.1.2 Exclusion criteria

- Uncontrolled diabetes as judged by the investigator.
- Subject who has received radiotherapy in the area of implantation, or such radiotherapy is planned during the study period.
- Current use of ototoxic drugs.
- Condition that could jeopardize osseointegration and/or wound healing or condition that may have an impact on the outcome of the investigation as judged by the investigator.
- Insufficient bone quality and quantity for implantation of a BI300 Implant, as determined by the surgeon.
- Unable to follow investigational procedures.
- Participation in another clinical investigation with pharmaceutical and/or device.

2.2 Number of subjects

Up to 20 subjects will be recruited for this study at 1 investigational site.

2.3 Duration of subject participation

Subjects will participate in a 12-month protocol in total.

2.4 Subject enrolment and informed consent/assent

As part of the informed consent and/or assent process, an investigator must explain the following to the potential investigational subject and/or the parent or legal guardian:

- The rationale, aims, and objectives of the investigation.
- Risks and benefits.
- Alternative treatments.
- Extent of the subject's involvement.
- That the subject can withdraw from the study at any time.
- That the confidentiality of patient data will be maintained at all times.
- That the subject and/or parent/legal guardian will be informed if new information becomes available that may be relevant to continued, willing participation in the trial.

The subject and/or parent/legal guardian must be provided the opportunity to ask any questions he/she/they might have. Signed and dated informed consent and/or assent must be obtained before any investigational procedure can be performed. A copy of the Informed Consent/Assent Forms shall be given to the subject and parent/legal guardian, when applicable.

The Sponsor and the Investigator(s) shall avoid improper influence on or inducement of the subject, monitor, the Investigator(s), or other parties participating in or contributing to the clinical investigation.

2.5 Subject Identification

To maintain confidentiality, the subject's name will not be recorded on any study document other than the informed consent form. All individuals who provide informed consent (sign the informed consent form) are considered consented into the study and will be assigned a unique identifier. A unique alphanumeric code will identify the subject throughout the course of the study. For example, CA01-OSI-0000, where:

- CA = Canada

- 01 = a sequential numeral corresponding the order in which a subject is enrolled into the study for a given study site, in this case this would correspond to the first subject recruited into the study for a particular site,
- OSI = an abbreviation for the study,
- 0000 = a unique, numeric study site identification.

2.6 Randomization

This is an open study with no comparator device. Randomization is not possible.

2.7 Completed Subjects

Each subject in the study will be considered completed when all assessments through 12 months postactivation have been performed in accordance with the study protocol. To be considered a primary endpoint success, subjects must retain their originally implanted device through the 6 month visit.

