2.10 Replacement of subjects

If a subject discontinues his/her participation in the investigation, he/she will not be replaced if this discontinuation occurs after surgery is performed. If this discontinuation occurs before surgery, the subject will be replaced in order to reach up to 20 evaluable subjects.

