3.2 Objectives and outcome measures

Primary objective	Outcome measure
To quantify the type and severity of adverse events in the pediatric population implanted with the Osia system.	Information will be collected from visit 2 through visit 7 of the trial.

Secondary objectives	Outcome measures
To collect surgical information.	
 • Soft tissue thickness • Soft tissue reduction performed • Type of anesthesia • Surgery time • Bone polishing/removal at the actuator site • BI300 Implant length • Location of BI300 Implant • Surgical incision type/location
To collect information about daily use of sound processor (dependent on child's ability to report).	
 • Daily usage time • SoftWear Pad use • Choice of magnet strength
To compare the self-reported assessments of hearing outcome with the investigational device and in a preoperative hearing situation.	
 • Speech, Spatial and Qualities of Hearing Scale -12 (SSQ-12) using the investigational device at 6 months postoperatively vs. the unaided condition preoperatively. • For children unable to complete the SSQ-12: Speech Spatial Questionnaire for Parents using the investigational device at 6 months postoperatively vs. the unaided condition preoperatively.

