6.2.3 Adverse Events of Special Interest (Osia Clinical Study only)

The following AEs are defined as adverse events of special interest (AESIs) and should be reported as soon as possible:

- AE that interferes with the daily use of the medical device(s).
- AE at the site of the implant that lead to:
 - Revision surgery including explantation.
 - Severe soft tissue complication.
 - Prescription of antibiotics.

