7.3 Risks associated with participation in the clinical investigation

Risks associated with participation in this study are anticipated to be similar for a child in relation to the adult population. The investigational device incorporates several components from already FDA and Health Canada approved products. There is no guarantee that the Osia Implant will not cause any adverse device events. The Osia Implant is expected to have a lifetime of about 10 years. As with any new surgical product and medical device, there is a risk that Unanticipated Adverse Event may occur. The subjects will be closely monitored in the investigation and instructed to contact the responsible investigator if they experience any untoward effect. In the worst-case

scenario, the patient would need a revision surgery to remove the Osia Implant. The subject will then end participation in the clinical investigation and follow normal clinical care and follow-up.

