8 DATA ANALYSIS

All subjects who are consented into the clinical study will constitute the intention-to-treat (ITT) population for the purposes of safety evaluation. Only subjects implanted with the Osia implant will be considered as the completed cases (CC) population and per protocol (PP).

Since the primary intent of this study is to provide preliminary safety and efficacy information, no formal hypotheses or sample size estimates were derived for this study.

Demographic and outcomes data for primary, secondary, and ancillary objectives will be tabulated individually along with group summary descriptive statistics where relevant.

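### Section 2.7 sets a 6-month device-retention condition for a primary success that no objective or analysis defines, and section 8 evaluates safety in all consented subjects although the primary objective concerns implanted children

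*Protocol*

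**What the plan says.** Section 2.7, after defining completion, adds: "To be considered a primary endpoint success, subjects must retain their originally implanted device through the 6 month visit".

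The primary objective, identical in the synopsis and section 3.2, is to describe which adverse events occur in implanted children and how severe they are. Its outcome measure is one sentence: "Information will be collected from visit 2 through visit 7 of the trial". In the Study Test Schedule, visit 2 is surgery, visit 6 is the 6-month visit and visit 7 the 12-month visit. Section 6.2.3 makes an implant-site event of special interest if it leads to, among other things, "Revision surgery including explantation".

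Section 8 states no hypothesis and plans individual tabulation with descriptive summaries. On populations it says: "All subjects who are consented into the clinical study will constitute the intention-to-treat (ITT) population for the purposes of safety evaluation". The next sentence reads: "Only subjects implanted with the Osia implant will be considered as the completed cases (CC) population and per protocol (PP"). Section 2.5 counts a subject as consented on signing the form. Section 2.10 adds, for children who drop out: "If this discontinuation occurs before surgery, the subject will be replaced in order to reach up to 20 evaluable subjects".

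On completion, section 2.7 says: "Each subject in the study will be considered completed when all assessments through 12 months postactivation have been performed". On removal of the implant, section 7.3 says: "The subject will then end participation in the clinical investigation and follow normal clinical care and follow-up".

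**The concern.** With no hypothesis and at most about 20 children, the adverse event summary is the study's main result. Its endpoint, time frame and population should therefore be stated once and consistently.

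Two statements work against that. The success sentence in 2.7 introduces a binary outcome that the objectives do not contain, at a time point that is not the end of the primary window. It invites a success percentage in the report that the objectives do not support and that is blind to device loss after visit 6. The safety population in section 8 is wider than the population in the primary objective. Followed as written, it would count children who never received the device in any proportion quoted for the device's safety.

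**Working it through.** The protocol gives no alpha, power or derived sample size, and no figure on this point to reproduce. The check is a comparison of sections, with arithmetic to size the two effects.

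**1. Is a success or retention endpoint defined anywhere?**

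- Primary (synopsis, 3.2): adverse events, visit 2 through visit 7. No success criterion and no 6-month point.
- Secondary (3.2): surgical data, daily use, and self- or parent-reported hearing at 6 months. No retention measure.
- Ancillary (3.2.1): free-field thresholds and word recognition at 6 months. No retention measure.
- Section 8: descriptive tabulation. No responder or success analysis.

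The term occurs only in 2.7. The 6-month point belongs to the hearing comparisons, not to the primary outcome.

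**2. How much of the primary window lies after visit 6?**

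Inputs from the schedule: visit 6 at 6 months ± 3 weeks, visit 7 at 12 months ± 4 weeks. Taking 12 months as 365.25 days, 6 months is 182.6 days.

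- Nominal: 365.25 − 182.6 = 182.6 days = 26.1 weeks, 50% of the window.
- Shortest: (365.25 − 28) − (182.6 + 21) = 337.25 − 203.6 = 133.6 days = 19.1 weeks; 133.6/337.25 = 39.6%.
- Longest: (365.25 + 28) − (182.6 − 21) = 393.25 − 161.6 = 231.6 days = 33.1 weeks; 231.6/393.25 = 58.9%.

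This measures elapsed time, not bias. As an illustration, assume 20 implanted and 1 to 3 explanted between visits 6 and 7. Then 20/20 = 100% meet the 2.7 condition, while 19/20 = 95.0% to 17/20 = 85.0% keep the device through visit 7.

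**3. Can the safety set exceed the implanted set?**

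Yes. Consent counts on signing (2.5), surgery comes later (visit 2), and those who leave before surgery are replaced (2.10). Each one adds to the consented set but not to the implanted set.

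**4. What does that do to a proportion?**

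An event proportion among implanted children is multiplied by n(implanted)/n(consented). Assume 20 implanted, 1 to 5 pre-surgery withdrawals, and 5 implanted children with an event:

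- Implanted: 5/20 = 25.0%.
- Consented, 1 withdrawal: 5/21 = 23.8% (factor 20/21 = 0.95).
- Consented, 5 withdrawals: 5/25 = 20.0% (factor 20/25 = 0.80).
- No withdrawals: no change.

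For scale, the exact 95% intervals are 8.7% to 49.1% for 5/20 and 6.8% to 40.7% for 5/25. The protocol plans no intervals. The shift is small against that uncertainty, but it always goes towards a lower rate.

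**The case against.** The best defence is that nothing planned depends on either statement. Section 8 contains no success analysis, so the 2.7 condition feeds no output, and a condition that must be met is not a full definition of success. No adverse event rate or denominator is specified. Results are to be tabulated individually, the implanted set is identified in section 8, and an all-consented set fits the recording of events from enrolment in 6.2.7.1. Which set heads which table is often left to a statistical analysis plan, which is not at hand here.

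Much of this stands and limits the size of the point. It does not remove it. An unused success condition tied to the word primary is still a conflict inside the protocol. The population for safety evaluation is not left open: section 8 fixes it, and fixes it differently from the primary objective.

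Three stronger readings are not supported:

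- A reader might infer that explantation after 6 months escapes the safety results. It does not: adverse events are scheduled through visit 7, and implant-site events leading to explantation are of special interest under 6.2.3.
- A reader might infer that the primary window is undefined because 6.2.7.1 lets recording run on to product approval. Section 3.2 fixes the window for the primary outcome; 6.2.7.1 governs only recording.
- A reader might infer that sections 2.7 and 8 contradict each other on completion, since an explanted child leaves the study under 7.3 yet was implanted. That holds only if section 8 means that every implanted subject is a completed case. Its wording can equally make implantation a necessary condition, which is compatible with 2.7. The text is ambiguous, not contradictory.

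**Conclusion.** The point holds on two counts. Section 2.7 sets a 6-month condition for a primary success that no objective or analysis defines and that does not match the primary window to 12 months. Section 8 assigns safety evaluation to a set that can include children who never received the device, while the primary objective concerns implanted children.

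The consequences are limited. The first affects no planned analysis and hides no event; the risk is an unsupported success figure in the report. The second would move an assumed 25.0% to between 23.8% and 20.0% with 1 to 5 pre-surgery withdrawals, would move nothing without withdrawals, and can be undone from the individual listings. The withdrawal, event and late-explant counts are all assumptions; the protocol gives none. The correction is worth making because it concerns the main result and requires only wording. Whether a completed case must also be complete in the sense of 2.7 is a secondary ambiguity.

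**What to change.** - Section 2.7: delete the success sentence, or list device retention in 3.2 as a separate descriptive outcome with its own time point and population.
- Section 8: name implanted subjects as the set for the primary adverse event summary, covering visit 2 through visit 7.
- So that no event is lost, list separately: events before surgery; events in consented subjects who were not implanted, including any whose surgery was started; and events after visit 7. Keep the all-consented summary as a supplement.
- Section 8: say whether a completed case must also satisfy the definition of completion in 2.7.

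This costs protocol wording only, with no added visits, subjects or data. If the plan is already approved, it needs an amendment that is signed under 10.5.1 and approved under 9.3.

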2.8 Discontinued Subjects

Any subject may voluntarily discontinue the study at any time without prejudice. The Investigator may discontinue a subject from the study at any time if (s)he considers that remaining in the study compromises the subject's health or the subject is not sufficiently cooperative. In either event, reason(s) for discontinuation should be recorded on a study withdrawal form, provided as part of the CRFs for the study.

Possible reasons for study discontinuation include the following:

- AE necessitating discontinuation from the study.
- The subject is lost to follow-up.
- Voluntary decision to withdraw consent made by the subject².
- Investigator decision³.
- Other reason.

In case of a subject lost-to-follow-up, the Investigator must attempt to contact the subject (or relative/family contact) by phone, email or letter at least three times. If attempts are unsuccessful, the 'subject withdrawal' form is to be completed in the study file and reported, as appropriate, in required reports to the Sponsor, Ethics and Health Canada.

² Withdrawal of consent is defined as the subject's voluntary decision to revoke consent to continue participation in the study.

³ Subject withdrawal from the study is defined as an Investigator decision. The Investigator may elect to withdraw a subject from the study at any time if he/she considers that remaining in the study compromises the patient's health or if the Investigator considers the subject lost to follow-up.

2.9 Premature Study Termination

Subjects are free to discontinue their participation in the investigation at any time.

- Subjects may be discontinued from the investigation at any time at the discretion of the investigator.
- There may be other reasons for subject withdrawal or discontinuation, e.g., implant loss.

Subjects who themselves discontinue from the investigation should always be asked about the reason(s) for the discontinuation and the presence of any adverse events. If possible, the subject should always be seen and assessed by an investigator. Any adverse event should be followed up.

2.10 Replacement of subjects

If a subject discontinues his/her participation in the investigation, he/she will not be replaced if this discontinuation occurs after surgery is performed. If this discontinuation occurs before surgery, the subject will be replaced in order to reach up to 20 evaluable subjects.

3 DESIGN OF THE CLINICAL INVESTIGATION

This clinical investigation is an open, prospective, single center clinical investigation with a duration of 12 months. Performance for each subject at 6 months postoperative will be compared to his/her own preoperative unaided hearing situation.

3.1 Justification for the design of the clinical investigation

The primary intent for this study involves the collection of preliminary safety and efficacy information on children, 5 through 18 years, implanted with the Osia system.

3.2 Objectives and outcome measures

Primary objective	Outcome measure
To quantify the type and severity of adverse events in the pediatric population implanted with the Osia system.	Information will be collected from visit 2 through visit 7 of the trial.

Secondary objectives	Outcome measures
To collect surgical information.	
 • Soft tissue thickness • Soft tissue reduction performed • Type of anesthesia • Surgery time • Bone polishing/removal at the actuator site • BI300 Implant length • Location of BI300 Implant • Surgical incision type/location
To collect information about daily use of sound processor (dependent on child's ability to report).	
 • Daily usage time • SoftWear Pad use • Choice of magnet strength
To compare the self-reported assessments of hearing outcome with the investigational device and in a preoperative hearing situation.	
 • Speech, Spatial and Qualities of Hearing Scale -12 (SSQ-12) using the investigational device at 6 months postoperatively vs. the unaided condition preoperatively. • For children unable to complete the SSQ-12: Speech Spatial Questionnaire for Parents using the investigational device at 6 months postoperatively vs. the unaided condition preoperatively.

3.2.1 Ancillary Objectives and Measures

Ancillary measures are additional measures that will be captured only if the child is capable of completing or performing the evaluation as determined by the Investigator.

Ancillary objective	Outcome measures
To compare unaided hearing performance preoperatively to aided hearing performance using the investigational device postoperatively	
Audiometric: Free-field thresholds (PTA4; mean of 0.5, 1, 2, and 4 kHz) using the investigational device at 6 months postoperatively vs. the unaided condition preoperatively.
 
Speech Perception: Aided monosyllabic words in quiet (% correctly perceived words at 60 dBA) using the investigational device at 6 months postoperatively vs. the unaided condition preoperatively.

4 PROCEDURES

Procedures performed during the clinical investigation are outlined in the flow chart, under **Study Test Schedule**.

4.1 Test equipment

The test set-up regarding speaker placement, sound room facility and software used at each clinic shall be checked and approved by the Sponsor during the site initiation visit. All tests shall be performed in the sound-isolated room. Equipment used for audiological testing shall be calibrated before initiation of the investigation. Calibration certificates will be asked for by the Sponsor as part of the study documentation.

4.2 Demographics

The following demographic data will be recorded at visit 1:

- Age collected as date of birth (month and year).
- Gender.
- Ethnicity.
- Nicotine use, if applicable.

4.3 Medical history

The following information will be recorded at visit 1:

- Relevant medical and surgical treatment as judged by the investigator.
- Current concomitant medication and treatments.

4.4 Baseline characteristics

During visit 1, a number of baseline characteristics will be recorded:

- Treatment ear (indicate left or right).
- Type of hearing loss: (Conductive, Mixed, or SSD).
- Etiology: (chronic) infection, tumor, trauma, otosclerosis, unknown.
- Current hearing aid (yes/no, specify model, side and years of hearing aid use, reason for change).
- Previous experience from amplified sound through a non-surgical solution (yes/no, specify type, years of aid in use, when stopped use, reasons stop using).
- Has the subject previously been suggested a bone conduction hearing implant (BCHI) solution (yes/no, reason for rejection).

4.5 Preoperative Audiometric Assessments

Preoperative unaided audiometric threshold measures (including both air and bone conduction thresholds) should demonstrate that the subject has a conductive, mixed hearing loss or single-sided sensorineural deafness and meets the audiological inclusion criteria.

An existing audiogram is acceptable, as long as it has been completed during the last 6 months, and contains all the required frequencies (minimally air and bone conduction at 500, 1000, 2000, and 4000 Hz) per protocol. The subject's pre-operative PTA4 (pure-tone average of 500, 1000, 2000, and 4000 Hz) should be computed and recorded to ensure the subject meets the inclusion criteria.

If an audiogram is older than 6 months and/or does not contain required frequencies, an entirely new audiogram should be performed at visit 1. Contralateral masking should be used, if needed, according to local practice. The hearing care professional shall always record the unmasked threshold and record the masked threshold, if applicable.

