6.2.4 Clinically significant threshold shifts

Shifts in threshold, relative to the preoperative baseline, will be reported as an adverse event (AE) when a shift at any frequency exceeds 15 dB HL.

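### An existing audiogram up to 6 months old can be the only preoperative bone-conduction baseline, so a change above 15 dB that arose before surgery can be recorded as a postoperative adverse event, or a real loss can be masked

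*Protocol*

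**What the plan says.** Section 4.5 (Preoperative Audiometric Assessments) is written around eligibility. It states that "An existing audiogram is acceptable, as long as it has been completed during the last 6 months", provided it covers "minimally air and bone conduction at 500, 1000, 2000, and 4000 Hz". A fresh test is conditional: "If an audiogram is older than 6 months and/or does not contain required frequencies, an entirely new audiogram should be performed at visit 1".

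The Study Test Schedule shows one preoperative audiogram, at visit 1. It shows none at visit 2 (surgery), and bone-conduction-only audiograms at visits 4 to 7. Visit 1 has no time point and no window relative to surgery. The other preoperative hearing measures, free-field thresholds and word recognition, are ancillary and do not measure bone conduction.

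Section 6.2.4 then uses the preoperative measurement as a safety reference. The rule concerns "Shifts in threshold, relative to the preoperative baseline", and such a shift "will be reported as an adverse event (AE) when a shift at any frequency exceeds 15 dB HL". The section does not say which audiogram is the baseline or how recent it must be. Section 3.2 makes the type and severity of adverse events, from visit 2 through visit 7, the only primary objective.

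**The concern.** A rule that suits eligibility has become, by default, the rule for the safety reference. To decide whether a child qualifies, a 6-month-old audiogram is reasonable. To decide whether hearing changed after implantation, the reference should lie close to the operation, because whatever happened between the old record and surgery is otherwise included in the difference.

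The error can go either way. If bone conduction worsened before surgery, part or all of the measured shift is preoperative, yet it appears as an event in the postoperative window. If the old record was taken in a temporarily worse phase, a genuine postoperative loss is measured from too high a starting threshold and may never reach 15 dB. In that case no event is raised for anyone to assess. Each child is his or her own control (section 1.4), so no comparison group shows how much change to expect without an implant. An analysis plan cannot recover a baseline that was not measured.

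**Working it through.** The protocol states no error rate or sample-size figure that could be reproduced; section 8 says none was derived. The check is a trace through the text, then the age of the baseline, then an illustration on stated assumptions.

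**Trace**

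1. Section 4.5: a complete audiogram from the last 6 months replaces the visit 1 test. The reference date is not stated; I read it as visit 1, because that is when an over-age record must be replaced.
2. Study Test Schedule: no further preoperative bone-conduction test, and no maximum interval from visit 1 to surgery.
3. Section 6.2.4: shift above 15 dB at any frequency from the preoperative baseline = adverse event.
4. Section 3.2: adverse events are the primary outcome.

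No section requires a repeat test near surgery or sets aside a shift that arose earlier.

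**Age of the baseline** (1 week = 7/30.44 = 0.23 months)

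Age at a visit = 6 months + gap from visit 1 to surgery + time since surgery.

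With the oldest permitted record and no gap:

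- At surgery: 6 months.
- Visit 4, early edge (4W − 1W = 3 weeks): 6 + 21/30.44 = 6.7 months, of which 0.69 (10%) is postoperative.
- Visit 4, late edge (4W + 1W = 5 weeks): 6 + 35/30.44 = 7.1 months, of which 1.15 (16%) is postoperative.
- Visit 7, late edge (12M + 4W): 6 + 12 + 28/30.44 = 18.9 months.

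A gap between visit 1 and surgery adds directly. An assumed gap of 3 months gives 9 months at surgery, 10.1 at the late edge of visit 4 and 21.9 at the late edge of visit 7.

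**Illustration of both errors**

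Assumptions, none from the protocol: test-retest differences are normal with SD σ of 5 or 7 dB; the four frequencies are independent; thresholds are recorded in 5 dB steps; shift means worsening. A recorded shift above 15 dB then means 20 dB or more, that is, an underlying difference above 17.5 dB. With net true change μ between baseline and test at all four frequencies, the chance of a flag at one audiogram is

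P = 1 − [Φ((17.5 − μ)/σ)]⁴

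| Net change μ from baseline | σ = 5 dB | σ = 7 dB |
|---|---|---|
| 0 dB | 0.1% | 2.5% |
| 5 dB | 2.5% | 14.0% |
| 10 dB | 24.2% | 45.8% |
| 15 dB | 77.1% | 83.3% |
| 20 dB | 99.1% | 98.3% |

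*False event:* with no surgical effect, a child whose hearing worsened by 10 dB before surgery is flagged with probability 24.2% to 45.8%, against 0.1% to 2.5% with no preoperative change.

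*Masked event:* a true postoperative loss of 20 dB is flagged with probability about 98% to 99% from an accurate baseline. If the old record was 10 dB too poor, the net change is 20 − 10 = 10 dB and the probability falls to 24.2% to 45.8%.

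The table shows sensitivity to a wrong baseline. It does not say how many children would have one.

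**The case against.** The strongest reply is that the protocol limits the damage. Section 6.2.7 records the onset date and the investigator's view of the relationship to device or procedure, and asks for supplemental investigations where they help establish causality. Adverse events are meant to be captured whether or not related (section 6.2.1). Section 8 has no hypothesis test to distort and tabulates subjects individually. This stands in part: a false event can be judged unrelated. But it still counts in an outcome covering all adverse events, the investigator has no near-surgery threshold on which to base the judgement, and a masked loss never reaches assessment.

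Several stronger readings are tempting and are not supported:

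- *That every change before surgery becomes an adverse event.* Only a measured shift above 15 dB does, and only children using an existing audiogram are exposed to its age.
- *That the wait for surgery is unlimited.* No per-child limit is stated, but section 10.8 plans the last visit in Q4 2018. With visit 7 at 12M ± 4W, surgery would fall by about 28 January 2018, some 5 months (151 days) after the protocol date of 30 August 2017. This is a study-level plan, so it bounds the expected delay without setting a rule.
- *That 4 visits × 4 frequencies × 20 children = 320 comparisons measures the problem.* A fresh baseline would give the same number of comparisons.
- *That the listed causes prove instability.* "Etiology: (chronic) infection, tumor, trauma, otosclerosis, unknown" is a set of recording categories in section 4.4. It says nothing about how thresholds change or how many children have each cause.
- *That existing audiograms come from uncalibrated equipment.* Section 4.1 says "All tests shall be performed in the sound-isolated room" and requires calibration before the study starts. An existing record may predate those checks, but the protocol does not say that it was made under other conditions.

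**Conclusion.** The concern holds as a weakness of design. The protocol permits an audiogram up to 6 months old to be the only reference for its one numeric adverse-event rule, and nothing elsewhere supplies a later preoperative bone-conduction measurement. For a child with the oldest permitted record and no delay to surgery, roughly 84% to 90% of the interval behind the visit 4 comparison is preoperative.

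How many of the up to 20 children would use an existing audiogram, and how often bone conduction changes by more than 15 dB in that time, cannot be derived from the protocol. The flag probabilities rest on the assumed retest SDs and assumed changes. The point therefore justifies a cheap improvement. It does not show that the primary outcome will be wrong.

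**What to change.** 1. In section 4.5, keep the 6-month allowance for eligibility screening only.
2. At visit 1, measure study-ear bone conduction at 500, 1000, 2000 and 4000 Hz in every child on the study equipment.
3. In section 6.2.4, name this measurement as the preoperative baseline.
4. In the Study Test Schedule, state a maximum interval from visit 1 to surgery, chosen by the sponsor, after which the four thresholds are repeated before surgery.

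The cost is a slightly longer visit 1 for children who would have relied on an existing audiogram, and a repeat test for any child whose surgery falls beyond the chosen interval. The schedule already lists an audiogram at visit 1, so no new visit is needed unless that repeat has to be arranged separately.
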